5. TREATMENT PLAN

5.1 Agent Administration

Treatment will be initiated on an inpatient basis. Reported adverse events and potential risks are described in Section 7. Appropriate dose modifications are described in Section 6. No investigational or commercial agents or therapies other than those described below may be administered with the intent to treat the patient's malignancy. The cycle length is 42 days for all dose levels.

Treatment will consist of the combination of blinatumomab and nivolumab, with or without ipilimumab per the dose escalation schedule below. A run-in of blinatumomab (10 days with planned dose escalation on day 8) prior to combination therapy will be incorporated at all dose levels to help determine the effect of blinatumomab on immune regulatory pathways in leukemia and as a means of minimizing the potential for overlapping toxicities, as many of blinatumomab's most significant side effects occur within the first few days of administration or after a dose increase. Nivolumab with or without ipilimumab will start on day 11 of cycle 1. When nivolumab and ipilimumab are scheduled on the same day, nivolumab should be given first followed by ipilimumab as described in Section 5.3.4

Pre-treatment phase (pre-phase): Pre-phase treatment with dexamethasone 10 mg/m² (maximum total 24 mg per day intravenously) for up to 5 days for patients with bone marrow blasts more than 50%, peripheral blood blasts of 15,000/ μ L or higher, or elevated lactate dehydrogenase suggesting rapidly progressing disease as per investigator's assessment is required unless other cytoreductive measures as outlined below have already been successfully implemented. Pre-phase treatment should be completed at least 24 hours before starting blinatumomab (study treatment). Other pre-phase treatment for cyto-reduction including cyclophosphamide, 6-MP, hydroxyurea, or corticosteroids (dexamethasone, prednisone or similar) (in patients not meeting the aforementioned criteria) may be used at the investigator's discretion but must be completed at least 24 hours prior to blinatumomab infusion.

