9. BIOMARKER, CORRELATIVE, AND SPECIAL STUDIES

9.1 Overview

Mandatory research bone marrow aspirates (40 cc-4 green top tubes-sodium heparin) and research peripheral blood specimens (preferred 100 cc [minimum 60 cc]-10 (min 6) green top tubes-sodium heparin) will be obtained (preferentially on the same day): at baseline (1-7 days prior to the initiation of study treatment; up to 14 days prior to the initiation of study treatment allowed for patients requiring prephase treatment), prior to first dose of nivolumab / ipilimumab in cycle 1 (day 8-11 +/- 4 days), at the end of cycles 1 and 2 (day 29-35), and every 3-4 months up to 1 yr, or at the time of relapse or off study.

Additional research peripheral blood specimens (preferred 40 cc [minimum 30 cc]- 3 or 4 green top tubes) will be collected in cycle 1 (days 1, 15, and 22; all ± 3 days), and prior to cycle 2 (day 40-42 of cycle 1).

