Writing Test ¹⁰	X	X	X		X	X ¹⁰				
EKG ¹¹ and ECHOcardiogram	X									
BM Aspirate and Biopsy ¹²	X		X (within 3 days prior to 1 st nivolumab)	X			X ¹² (end Cy 2; every 3-4 mos up to 1 year)	X ¹² (every 3-4 months up to 1 year)		X ¹² (off treatment or relapse)
MRD Monitoring ¹²	X		X	X			X ¹²	X ¹²		X
LP and CSF analysis with Intrathecal Chemotherapy ¹³	X			X			X ¹³ (cy 2 only required)	As per investigator's discretion	As per investigator's discretion	

Correlative Studies from BM (Section 9.1 and Appendix E for instructions) ¹⁴	X		X (within 3 days prior to nivo)	X			X ¹⁴	X ¹⁴		X ¹⁴
Correlative Studies from PB (Section 9.1 and Appendix E for instructions) ¹⁵	X	X	X	X	X	X	X	X (every 3-4 months up to 1 year)		X ¹⁵ (off treatment or relapse)
Symptom/Toxicity Assessment ¹⁶	X	X-----X ¹⁶ See specific requirements for monitoring after last dose of nivolumab and/or ipilimumab, and after allo-HSCT ¹⁶								
Follow-up/Survival ¹⁷									X ¹⁷	X ¹⁷

¹ Ipilimumab will be administered every 6 weeks and only to subjects treated on DL B1 (B-1) and B-2. Both Ipilimumab and Nivolumab can be given ± 2 days from the scheduled time and delayed in Cycle 1 up to day 25 as defined in Section 5.3.2 and 5.3.3.
 
² Interim history/physical exam and vital signs (heart rate, blood pressure, temperature, respiratory rate and O2 saturation) will be performed prior to each cycle, weekly during cycle 1 and 2, and every 2 weeks in cycle ≥3. During cycle 1 patient are expected to be hospitalized for 14 days and in subsequent cycles for the first 2 days and will have daily history/physical exam/vital signs (including S02) as per standard of care (SOC). Vital signs (including S02) will be monitored prior to start of each nivolumab and ipilimumab infusion and at the end of infusion or more frequently as indicated. Height will be recorded only prior to start of treatment on the study. Weight and performance status will be measured/assessed prior to each cycle (every 6 weeks).
 
³ CBC and differential will be performed on day 1 of each cycle, daily for the first 4 days of cycle 1, weekly during cycle 1 and 2, and every 2 weeks thereafter for the duration of therapy. CBC and diff should be performed within three days of nivolumab and ipilimumab administration. The frequency of CBC/diff measurements may be higher and adjusted for individual patient’s need as per the SOC requirements for monitoring and treatment of patients with ALL.
										

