¹¹ All patients should have baseline ECG. Baseline ECHOCardiogram is required for patients with a history of CHF, or at risk because of underlying cardiovascular disease (e.g history of angina, heart attack, or prior cardiovascular interventions or findings), history of cardiac arrhythmias, or exposure to cardiotoxic drugs (e.g anthracyclines, cyclophosphamide, or others) as clinically indicated. Any patient with heart arrhythmia or ischemic changes on baseline ECG should have baseline ECHOCardiogram. In addition, any patient who develop symptoms or signs of CHF, MI, cardiomyopathy, or myositis in the course of the study, should have repeat EKG, ECHOCardiogram, as well as cardiac evaluation including lab tests, CPK, troponin, and cardiology consultations as clinically indicated.

¹² Bone marrow aspirate and biopsy to assess disease status and response to therapy will be performed at baseline (after pre-registration and prior to registration), at the end of cycle 1 and 2 (day 29-day 35), and every 3-4 months thereafter up to 1 yr, any time relapse is suspected or off treatment. Additional bone marrow aspirates for research purposes only will be performed in cycle 1 within 3 days of the first nivolumab/ipilimumab administration (between days 8-11 of cycle 1 but can be delayed if nivolumab and/or ipilimumab administration is delayed in Cycle 1 as per Section 5.3.2 and 5.3.3) prior to nivolumab administration. Each time bone marrow assessment is performed to assess disease status, the flow cytometry studies for MRD assessment will be performed.

¹³ All patients should have baseline CSF assessment prior to enrollment on the study. Administration of intrathecal chemotherapy is required when LP is performed with a choice of agent (ara-C or MTX or both) and dose as per institutional standard of practice. Subsequent IT chemotherapy administration for CNS prophylaxis should be performed at the end of blinatumomab administration in cycles 1 and 2 (day 29-35) and the determination of need for subsequent CSF prophylaxis will be per investigator's discretion.

¹⁴ Each time bone marrow is performed for disease status assessment additional 40 cc of the bone marrow should be collected for research studies. Additional bone marrow aspirate for research purpose only will be performed in cycle 1 (between days 8-11) prior to nivolumab administration.

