11.1.4 Response Criteria

Responses will be assessed at the conclusion of cycles 1 and 2 and in follow-up given the response definitions provided above.

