13. STATISTICAL CONSIDERATIONS

13.1 Overall

This is a multi-site, open-label, Phase 1 study of evaluating safety, tolerability, and preliminary antitumor activity of blinatumomab and nivolumab with or without ipilimumab in patients with CD19+ Pre-B ALL and CD19+ MPAL. The study consists of two parts: dose escalation for blinatumomab and nivolumab with and without ipilimumab and dose expansion at MTD. The dose expansion cohort will only be initiated once the MTD for the combination therapy has been established. In each part of the study, a ten-day run-in of blinatumomab prior to combination therapy will be incorporated to help determine the effect of blinatumomab on immune-related parameters of each patient's leukemia.

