13.8 Analysis of Exploratory Endpoints

13.8.1 Characterizing T cell populations

The analyses of pre- and post-treatment PB and BM specimens for immune parameters will be descriptive and graphical in nature. Data will be summarized for each patient group separately (blinatumomab plus nivolumab; blinatumomab plus nivolumab and ipilimumab). Flow values at each time point will be summarized using geometric means and standard deviation. Differences in baseline values between patient subgroups will be explored using linear regression models. We are specifically interested in determining what pretreatment signature is associated with outcome, such as having a complete response or becoming refractory. To this end, we will use logistic regression models with ROC analysis to describe which pretreatment parameters are potential predictors of outcomes following treatment. Values will be checked for skewness and log-transformed as appropriate. The change in flow values at each time point after blinatumomab and blinatumomab plus checkpoint inhibitor(s) relative to the baseline value will be modeled using mixed-effects, linear regression models that include fixed effects for time point and a random effect for the patient to account for within-patient correlation of measurements. Post-treatment changes in T cell populations will be correlated with clinical outcomes such as CR vs. No CR or MRD vs. No MRD using interaction tests. T cell subsets in the PB and BM defined by multicolor flow cytometry will be summarized before and after treatment with blinatumomab alone or plus checkpoint inhibitors by treatment group using summary statistics. Differences in T cells before and after treatment will be explored using non-parametric Wilcoxon signed rank tests or paired t tests as appropriate. The expression of co-inhibitory/-stimulatory molecules will also be examined in the same way.

13.8.2 Characterization of T cell transcriptional signature before and after treatment.

Expression levels will be summarized at pre-treatment and post-treatment using standard descriptive statistics. Differentially-expressed genes and corresponding fold-changes will be analyzed using standard statistics and through the use of Ingenuity pathway analysis as described previously. We will identify differentially-expressed genes by patient subgroups such as CR v. NR and MRD v. No MRD using interaction tests.

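### MRD at the pre-nivolumab marrow is marked in the calendar grid but not supported by its footnotes or used in any analysis, and flow summaries of the common blinatumomab run-in are split by treatment group

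*Combined protocol and SAP*

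**What the plan says.** **Calendar.** In Table 10.1 (Section 10) the row "MRD Monitoring" has a mark at screening, in cycle 1 weeks 2-4 and in cycle 1 weeks 5-6. The marrow row places the weeks 2-4 marrow within 3 days before first nivolumab. Footnote 12 says: "Additional bone marrow aspirates for research purposes only will be performed in cycle 1 within 3 days of the first nivolumab/ipilimumab administration". Footnote 14 repeats the research-only status. Footnote 12 then requires MRD flow whenever a marrow is done to assess disease status.

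**Response and MRD analysis.** Section 11.1.4: "Responses will be assessed at the conclusion of cycles 1 and 2 and in follow-up". Section 13.3.2.2 reports MRD status among clinical responders by arm and dose level. Section 13.7 reports CR, CRi and PD in the same way. None of the three refers to the end of the run-in.

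**Run-in.** Section 5.1 gives its purpose as "to help determine the effect of blinatumomab on immune regulatory pathways in leukemia and as a means of minimizing the potential for overlapping toxicities". Section 13.1 agrees: "a ten-day run-in of blinatumomab prior to combination therapy will be incorporated to help determine the effect of blinatumomab on immune-related parameters".

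**Immune analysis.** Section 13.8.1: "Data will be summarized for each patient group separately", the groups being the doublet and the triplet. It also says that T-cell subsets will be summarized by treatment group after blinatumomab alone as well as after the checkpoint inhibitors. The same section models change from baseline at each time point, with a fixed effect for time and a random effect for patient; no arm term is named. Section 13.8.4 summarizes cytokines for all patients and within subgroups.

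**The concern.** The trial has no blinatumomab-only arm. The time point just before the first checkpoint dose is therefore its only within-patient evidence of what blinatumomab had done by then. Two features of the plan weaken that evidence.

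First, the calendar contradicts itself on whether MRD is measured at that marrow. Some sites may send it for MRD and others not, and any result would have no place in the analysis. Effects on MRD belong to the first secondary objective (1.2.1), and Section 2.4.1 expects the combination to bring responses in patients who would not respond to blinatumomab alone.

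Second, patients in both groups are planned to receive identical treatment until the first checkpoint dose. Summarizing that period separately estimates one quantity twice, each time with fewer patients.

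**Working it through.** **A. The calendar, side by side**

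1. Weeks 2-4 of cycle 1 are days 8 to 28.
2. The end-of-cycle-1 marrow is on days 29-35 (footnote 12), so it belongs to the weeks 5-6 column.
3. The only marrow left in the weeks 2-4 column is the pre-nivolumab one. The MRD mark in that column can refer only to it.
4. Under footnotes 12 and 14 that marrow is for research. It is not a disease-status marrow, so footnote 12's MRD sentence does not reach it.
5. The grid therefore asks for MRD and the footnotes do not. Sections 11.1.4, 13.3.2.2 and 13.7 would not use the result in either case.

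**B. Precision of the run-in change**

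*The plan's own figure.* Section 13.5 gives a maximum of 36. Levels A1 and A-1 (6 + 6), B1 and B-1 (6 + 6) and two expansion cohorts (6 + 6) sum to 36, so it reproduces.

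*Group sizes.* Section 5.2.1 records A1 as the doublet MTD after 6 patients. With its expansion cohort the doublet has 6 + 6 = 12. The triplet has 6 + 6 = 12 if B1 is the MTD, and up to 6 + 6 + 6 = 18 after de-escalation to B-1. The pooled run-in then has 24 to 30 patients. The design maximum of 18 per group (36 pooled) is shown for completeness; it would have needed de-escalation in both parts.

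*Formula.* The half-width of the 95% interval for a mean paired change, in SD units of the change, is t(0.975, n-1)/√n.

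| n | calculation | half-width (SD) |
|---|---|---|
| 12 | 2.201/√12 | 0.635 |
| 18 | 2.110/√18 | 0.497 |
| 24 | 2.069/√24 | 0.422 |
| 30 | 2.045/√30 | 0.373 |
| 36 | 2.030/√36 | 0.338 |

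*Gain from pooling.*

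- Groups of 12 and 12: 1 - 0.422/0.635 = 34%.
- Groups of 18 and 18: 1 - 0.338/0.497 = 32%.
- Groups of 12 and 18: 1 - 0.373/0.635 = 41% for the smaller group and 1 - 0.373/0.497 = 25% for the larger.

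The documents give no SD for any flow marker, so no absolute figure is possible.

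**The case against.** **The run-in is used for its stated purpose.** A reader might infer that the plan ignores it. The documents do not support that. Sections 5.1 and 13.1 give the purpose as immune parameters and, in 5.1, limiting overlapping toxicity; neither names MRD or antileukemia effect. Section 13.8.1 models the post-blinatumomab time point against baseline, and Section 9.2.1.2 plans flow on leukemia blasts before the first checkpoint dose. This objection stands in full.

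**The split is narrower than it looks.** It applies to the descriptive flow summaries. The mixed model names no arm term, and cytokines are also summarized for all patients. This stands too. However, 13.8.1 does carry the by-group split to the blinatumomab-alone time point, so the need for clarification remains.

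**Early clearance does not settle attribution.** A reader might infer that a CR in a patient whose marrow had cleared before nivolumab owes nothing to nivolumab. That does not follow. Marrow clearance on days 8-11 is not CR, which under 11.1.2 also needs trilineage hematopoiesis, neutrophil and platelet recovery and no extramedullary disease. A checkpoint inhibitor may still deepen or prolong a response. Nor does residual disease at that time show that a later response was due to nivolumab. Reporting CR by assigned regimen is ordinary single-arm practice, and 13.7 makes no add-on claim.

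**Pre-phase and the baseline.** For pre-phase patients the baseline sample may be taken "up to 14 days prior to the initiation of study treatment allowed for patients requiring prephase treatment" (9.1), so steroid or cytoreductive effects can enter the change from baseline. Substituting the cycle 1 day 1 blood sample is not a ready remedy. Its window is ±3 days in 9.1 and footnote 15 and -3 days only in Appendix F, so it need not be pre-infusion. Dexamethasone is also given before day 1 and before the day 8 step (5.3.1), and the marrow baseline would be unchanged.

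**Conclusion.** Two modest defects hold. The MRD row of Table 10.1 conflicts with footnotes 12 and 14, and no planned analysis would use an MRD result from the pre-nivolumab marrow. The 13.8.1 flow summaries divide by group a run-in that is planned to be identical in all patients; pooling would narrow the interval by about one third with equal groups, and by 25% to 41% with groups of 12 and 18.

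The precision figures assume complete baseline and pre-nivolumab pairs, a common mean and SD of change in both groups, and both expansion cohorts filled. The pooling argument also assumes similar sampling times. That needs checking, because Section 5.3.2 allows first nivolumab to move to day 15, or to about day 25.

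The documents do not support saying that the run-in goes unused, or giving a number of CRs that could not involve nivolumab. The point is minor: it touches secondary and exploratory endpoints and leaves safety, DLT assessment and the MTD unaffected.

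**What to change.** 1. **Reconcile Table 10.1 with footnotes 12 and 14.** If the marrow is to stay research only, remove the weeks 2-4 mark from the MRD row. If MRD is intended as the grid shows, add the pre-nivolumab marrow to footnote 12's MRD sentence and add to 13.7 a descriptive table of CR/CRi and MRD by residual disease at that marrow. State beside the table that early clearance is only a lower bound on blinatumomab's effect and does not show that the checkpoint inhibitors added nothing. State also that this read is not a response assessment for the efficacy evaluable set in 13.2, so that set does not change.
2. **Pool the run-in in 13.8.1.** Estimate the baseline-to-pre-nivolumab change once over all dose levels, record the actual sampling day, and separate the groups only after the first checkpoint dose.
3. **Optional.** Reconcile the cycle 1 day 1 blood window between 9.1, footnote 15 and Appendix F. Until that is done, the sample should not serve even as a sensitivity baseline for blood markers.

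**Cost.** Item 2 is wording only. Item 1 adds no procedure, since the aspirate is mandatory. An MRD read would still need its own routing, because Section 9.1.2 sends research marrow to a research laboratory for Ficoll processing and freezing, with batch shipment from some sites. Overall this is a free to cheap improvement.

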11. MEASUREMENT OF EFFECT

Although the clinical benefit of nivolumab and ipilimumab has not yet been established in ALL, the intent of offering this treatment is to provide a possible therapeutic benefit, and thus the patient will be carefully monitored for leukemia response and symptom relief in addition to safety and tolerability. Patients will be assessed by standard criteria. For the purposes of this study, patients will be re-evaluated with a bone marrow biopsy at the conclusion of the first and second cycle of treatment, at the end of the last blinatumomab containing cycle, and every 3-4 months thereafter, and off study. A bone marrow biopsy should also be obtained at anytime there is clinical suspicion for relapse based on changes in symptoms, exam, or laboratory parameters.

11.1 Antitumor Effect – Hematologic Tumors

11.1.1 Definitions

Evaluable for toxicity. All patients will be evaluable for toxicity from the time of their first treatment with blinatumomab.

Evaluable for objective response. Patients who have measurable disease present at baseline, have received at least one cycle of therapy, and have had their disease re-evaluated will be considered evaluable for response. These patients will have their response classified according to the definitions stated below. (Note: Patients who exhibit objective disease progression prior to the end of cycle 1 will also be considered evaluable.)

11.1.2 Disease Parameters

Complete Remission (CR)

- 1 No circulating blasts or extramedullary disease
 - No lymphadenopathy, splenomegaly, skin/gum infiltration/testicular mass/CNS involvement
- 2 Trilineage hematopoiesis (TLH) and <5% blasts
- 3 Absolute neutrophil count (ANC) >1,000/ μ L
- 4 Platelets >100,000/ μ L

CR with incomplete blood count recovery (CRi)

- Meets all criteria for CR except platelets and/or ANC

Refractory Disease

- Failure to achieve CR after 1-2 cycles of treatment

Progressive Disease (PD)

- Increase of at least 25% in the absolute number of circulating or bone marrow blasts or development of extramedullary disease

Relapsed Disease

- Reappearance of blasts in the blood or bone marrow (>5%) or in any extramedullary site after a CR

Minimal Residual Disease (MRD)

- MRD in ALL refers to the presence of leukemic cells below the threshold of detection by conventional morphologic methods. Patients who achieved a CR by morphologic assessment alone can potentially harbor a large number of leukemic cells in the bone marrow.

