5.3 Study Drugs

5.3.1 Blinatumomab

Blinatumomab will be administered as a continuous IV infusion over four weeks followed by a two-week treatment-free interval. It is recommended that patients are hospitalized at least during the first 14 days of the first cycle and the first two days of the subsequent cycles. The hospitalization time depends on the investigator's judgment, as well as safety and tolerability of blinatumomab.

Cycle 1: The planned initial dose of blinatumomab is 9 µg/day administered via continuous intravenous infusion on days 1-7 of the first 42-day cycle. If patients tolerate the initial infusion without significant adverse events, then the dose of blinatumomab will be escalated to 28 µg/day administered via continuous intravenous infusion on days 8-28 of cycle 1. There will be a minimum blinatumomab treatment-free interval of 14 days following the completion of blinatumomab infusion prior to the initiation of the next cycle. Patients will be eligible for up to five cycles of blinatumomab if they achieve complete remission (CR) or CR with incomplete hematologic recovery (CRh) following 1-2 cycles of treatment. Given that this is a group of patient with a very high risk ALL, patients will be eligible to proceed to allogenic HSCT at the treating physician's discretion at any time after a response is documented. For patients receiving **cycles 2-5**, the planned dose of blinatumomab is 28 µg/day to be administered via continuous infusion on days 1-28 of each 42-day cycle.

Blinatumomab should be infused at a constant flow rate using an infusion pump. The pump should be programmable, lockable, non-elastomeric, and have an alarm. Blinatumomab infusion bags should be infused over 24 or 48 hours according to the instructions on the pharmacy label on the bags (Section 8.1.1). The solution should be administered using IV tubing that contains a sterile, non-pyrogenic, low protein-binding, 0.2 micron in-line filter. The IV line should never be flushed, especially when changing bags or at the completion of infusion, due to the risk of excess dosage. Blinatumomab should be infused through a dedicated lumen. Nivolumab +/- ipilimumab will be infused through a separate line from blinatumomab to allow continuous blinatumomab infusion when nivolumab +/- ipilimumab are administered.

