11.1.5 Duration of Response

Duration of overall response: The duration of overall response is measured from the time criteria are met for CR or CRi (whichever is first recorded) until the first date that relapsed disease is objectively documented.

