13.3.2 Secondary Objectives

- 13.3.2.1 The frequency distribution of responses, including CR, CRi or progressive disease (PD) by treatment arm and dose level for all patients on study will be determined and reported with exact 95% confidence intervals.

- 13.3.2.2 For patients who have a clinical response, the frequency of MRD+ vs. MRD-responses will be reported by treatment arm and dose level for all patients on study.
- 13.3.2.3 For patients who have a clinical response, duration of response (DOR) will be analyzed as a time-to-event outcome with the duration being measured as the time from measured response to progressive disease, death, or study end.
- 13.3.2.4 Overall survival will be measured from the first day of treatment on the study until death or last known follow up.

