13.7 Analysis of Secondary Endpoints

The secondary objectives of this study include describing preliminary antileukemia activity of blinatumomab and nivolumab, and blinatumomab plus both nivolumab and ipilimumab, including the effects on MRD, and assessing preliminary antileukemia activity in an expansion cohort of patients with poor-risk, relapsed or refractory CD19⁺ Pre-B cell ALL. The frequency distribution of responses, including CR, CRi or progressive disease (PD) will be reported by treatment arm and dose level for all patients on study and reported with exact 95% confidence intervals. For patients who have a clinical response, duration of response (DOR) will be analyzed as a time-to-event outcome using the Kaplan Meier method with the duration being measured as the time from measured response to progressive disease, death, or study end. A sensitivity analysis may be performed to evaluate DOR while excluding patients who go on to have an allo-HSCT. Overall survival will be measured using the Kaplan Meier method as the time from the first day of treatment on the study until death or last known follow up.

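### Duration of response has two different end events, CRi counts as a response but not for refractory disease or relapse, and the continuation rules in 5.3 and 5.6 disagree

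*Combined protocol and SAP*

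**What the plan says.** **End of response.** Section 11.1.5 starts DOR at the first recorded CR or CRi and continues it "until the first date that relapsed disease is objectively documented". It mentions neither death nor PD. Sections 13.3.2.3 and 13.7 define DOR as the "time from measured response to progressive disease, death, or study end", and 13.7 applies the Kaplan-Meier method to it. Neither names relapse.

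**Disease states.** Section 11.1.2 lists CRi separately from CR: a CRi patient misses the platelet or neutrophil criterion. It then defines refractory disease as "Failure to achieve CR after 1-2 cycles of treatment". Relapse is the return of blasts in blood or marrow, or "in any extramedullary site after a CR". PD is a different category: "Increase of at least 25% in the absolute number of circulating or bone marrow blasts", or new extramedullary disease.

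**Continuation.** Section 5.3.1 lets patients go on to five blinatumomab cycles "if they achieve complete remission (CR) or CR with incomplete hematologic recovery (CRh) following 1-2 cycles of treatment". Sections 5.3.2 and 5.3.3 use the same CR-or-CRh condition for nivolumab and ipilimumab. Section 5.6 lists not being in complete remission by the end of cycle 2 as a reason to stop, and 5.8 takes patients off treatment when any 5.6 criterion applies.

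**Transplant.** Section 13.7 adds: "A sensitivity analysis may be performed to evaluate DOR while excluding patients who go on to have an allo-HSCT".

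**The concern.** These are operative definitions, and they give different instructions for the same patient. A responder who dies in remission has an event under 13.7 and no stated outcome under 11.1.5. A CRi patient is a responder under 11.1.5 and refractory under 11.1.2. A patient in CRi or CRh after cycle 2 may continue under 5.3 and must stop under 5.6 with 5.8.

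Deaths in remission are foreseeable. Section 5.3.1 allows responders to go to allogeneic transplant at any time after a response is documented, Section 13.4.2 says many patients will be transplant candidates, and that section monitors non-relapse mortality to day 100. The transplant sensitivity analysis is optional and removes patients; it does not say which end event is the main one. The exploratory contrasts in 13.8.1 and 13.8.2 (complete response against refractory, CR against no CR, CR against non-response) do not say where CRi belongs. If these points stay open until the data are in, the definitions will be chosen with the deaths and CRi cases in view.

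**Working it through.** The plan states no figure for DOR, so there is none to reproduce. The check sets the rules side by side and applies each literally.

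**1. DOR outcome by patient**

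| Patient | 11.1.5 with 11.1.2 | 13.3.2.3 and 13.7 |
|---|---|---|
| CR, then marrow blasts above 5% | Ends at relapse | Relapse not named; ends only if the change also counts as PD |
| CR, then death without relapse | No rule for death | Ends at death |
| CRi, then blasts return | Relapse needs a prior CR, so literally no end event | Relapse not named; ends only at PD or death |
| Responder alive without relapse at study end | No rule | Study end listed beside PD and death; censoring not stated |

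PD cannot simply be read as relapse: 11.1.2 defines the two separately, and 5.6 lists both.

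**2. Is CR shorthand for CR or CRi?** Sections 11.1.5, 13.3.2.1 and 13.7 name both states when both are meant, and 11.1.2 defines CR with count thresholds that CRi does not meet. No section says that CR includes CRi.

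**3. Continuation.** Section 5.3.1 equates complete remission with CR and sets CRh beside it as an alternative. If complete remission has the same meaning in 5.6, a CRh patient who may continue under 5.3.1 must stop under 5.6.

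**4. Illustration of the death rule.** Input: 5 responders, as in the 5 of 6 remissions that Section 5.2.1 reports at dose level A1. Assumptions: the first event is a death in remission, two relapses follow, nobody else is censored before them, relapse counts as the end event under both rules, and 11.1.5 is applied by censoring the death. At each event the estimate is multiplied by (n − 1)/n, with n at risk.

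- Death as an event (13.7): 4/5 = 80%; × 3/4 = 60%; × 2/3 = 40%.
- Death censored (11.1.5): 100%; × 3/4 = 75%; × 2/3 = 50%.

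**5. Illustration of how likely such a death is.** With k responders transplanted and independent non-relapse death risk p, the chance of at least one such death is 1 − (1 − p)^k. Both k and p are assumed; 20% is the non-relapse mortality limit in 13.4.2, not an expected rate.

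- p = 10%: k = 3 gives 1 − 0.9³ = 27%; k = 5 gives 1 − 0.9⁵ = 41%.
- p = 20%: k = 3 gives 1 − 0.8³ = 49%; k = 5 gives 1 − 0.8⁵ = 67%.

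**The case against.** The strongest reply is that the plan contains only one Kaplan-Meier analysis of DOR, in 13.7, and it already lists death. Section 11.1.5 describes when a response ends through disease and plans no analysis; that it would censor a death is an assumption. This stands as a limit. A reader might infer that the planned analysis leaves death undecided, and the documents do not support that: an analyst working from 13.7 alone counts death. What remains is that 11.1.5 contradicts it, that relapse is missing from 13.7, and that study end, probably meant as censoring, is listed like an event.

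On CRi, its full name in 11.1.2 begins with CR, and 11.1.5 plainly expects CRi patients to be able to relapse. The intention is therefore fairly clear, but the definitions of refractory disease and relapse do not carry it out. The documents do not say how many patients are in CRi.

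On continuation, 5.6 opens in general terms, 5.3.1 to 5.3.3 are the specific drug rules, and CRh as spelled out in 5.3.1 is close to CRi. This may be only a label mismatch. Section 5.8 nevertheless makes the 5.6 criteria binding, so a site still has two instructions.

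A reader might also infer that a trivial rise in blasts during remission would count as PD and end a response. The documents do not establish this: PD is stated as an absolute number with no reference point for a patient in remission, and 11.1.2 has a separate category, with a 5% threshold, for blasts that return after a CR.

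**Conclusion.** The inconsistency is real in all three places and should be corrected, but its reach is narrow. It affects the secondary DOR estimate, the exploratory contrasts of response against refractory disease, and whether a CRi or CRh patient stays on treatment after cycle 2. A reader might infer that the main results are compromised. They are not: DLT assessment, MTD, the stopping rules and the CR/CRi/PD frequency tables do not use these definitions of DOR, refractory disease or relapse.

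The conclusion rests on the wording alone. The Kaplan-Meier figures (40% against 50% after the third event) and the chances of a transplant-related death (27% to 67%) only show that the choice can be visible in so small a group. They depend on an assumed order of events, numbers transplanted and death rates, and do not predict this trial's results.

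**What to change.** - **11.1.5, 13.3.2.3 and 13.7:** use one definition. DOR runs from first CR or CRi to relapse or death from any cause; patients alive without relapse are censored at their last disease assessment.
- **11.1.2:** define refractory disease as failure to achieve CR or CRi, keeping the existing cycle wording, and relapse as occurring after CR or CRi.
- **5.6:** make the stopping criterion the absence of CR or CRi by the end of cycle 2.
- **5.3.1 to 5.3.3:** replace the undefined CRh with CRi, after the sponsor confirms that CRi as defined in 11.1.2 is meant. This needs a decision, because Section 2.2.1.2.2 uses CRh for partial hematologic recovery, while CRi in 11.1.2 sets no minimum counts. If the stricter state was intended, the substitution would widen who may continue; criteria for CRh would then have to be added to Section 11, and 5.6 matched to them.

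The cost is wording changes in Sections 5, 11 and 13. No new data or visits are needed: Section 5.7 already follows patients for relapse and survival every 3 months for 2 years after treatment.
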